##### 5.3. Graphical exploration of the data

Figure 1: Graphical presentation of concentration vs time since first dose

Figure 2: Graphical presentation of concentration vs time since second dose

The individual concentrations will be shown as scatters and a smoothed line will be drawn per dose group. These graphs will allow a visual comparison of concentrations from different dose groups with a comparable time since first / second dose.

As a MOCK for Figure 1 and 2:

[figure not shown]

Figure 3: Graphical presentation of rich concentrations vs time since first dose

Figure 4: Graphical presentation of rich concentrations vs time since second dose

For these graphs, the concentrations from a single subject will be connected and each dose group will be shown in a separate color.

As a MOCK for figure 3 and 4:

[figure not shown]
[figure not shown]

Figure 5: Graphical presentation of weight vs concentration

For this graph, the concentrations from a single dose group will be connected and weight is on the X-axis.

As a MOCK for Figure 5:

**5.4. Regression model**

Table 2: Regression on concentration

A regression analysis will be performed on concentration including time since first and second dose, weight and age as covariates; and dose group and sex as factors.

This table will present the LS-Means (and 95%CI) of the dose groups and Type III statistics for all variables in the model.

The model diagnostics will be looked at.

**5.5. Observation**

A conclusion as described in Section 6 will be drawn after close inspection and taking into account all information from this set of tables and figures. Dependent on the availability (eg. number of subjects with extensive PK sampling, distribution) and nature of the data (eg. outliers), other analyses may be performed such as comparison of concentrations matched on bins of time since first/second dose or non-parametric analysis.

**5.6. Software**

SAS version 9.2 will be used for programming.

**6. FORMAT OF ASSESSMENT**

The assessment that will be provided to the sponsor's Executive Committee will only contain general information on the relationship between ALX0171 dose groups and plasma concentrations in one of the following formats:

Based on the exploratory analysis of the data:

- 7. There is an increase in concentration with increasing dose
- 8. There is no increase in concentration with increasing dose
- 9. The relationship between dose and plasma concentration cannot be assessed

No detailed analysis results or statistical inferences will be provided to the sponsor at this time. The assessment and any follow up communication will be documented and filed in the study binder. This implies that no subject related data will be provided to the sponsor to ensure the blind is maintained.

**19.3 Appendix C: Major Protocol deviation criteria with potential impact on primary efficacy (Subset of the full trial Protocol deviations criteria list)**

Sequence No.	Description	Protocol Deviation Coded Term (DVDECOD)	Protocol Deviation Term (DVTERM)
1.	The subject is younger than 28 days of age or 2 years or older (>= 24.00 months) of age at the time of signing Informed consent form (ICF), but the subject was randomized. - or - The subject's gestational age at birth is less than 33 weeks, but the subject was randomized.	Selection criteria not met	Inclusion criterion 1 not met: Subject is <specify age in months/days> old at date of informed consent. - or - Inclusion criterion 1 not met: Subject's gestational age is <specify age> weeks at birth.
2.	The subject's weight at screening is less than 3.0 kg or 15.0 kg or more, but the subject was randomized.	Selection criteria not met	Inclusion criterion 2 not met: Subject's weight at screening is not between 3.0 and 15.0 kg.
3.	Apart from a clinical diagnosis with RSV LRTI including typical RSV symptoms, the subject is not healthy at screening, but the subject was randomized.	Selection criteria not met	Inclusion criterion 3 not met: Subject is not healthy, apart from the clinical RSV diagnosis.
4.	For subjects enrolled under Protocol v2.0: The subject does not have a positive RSV diagnostic test, but the subject was randomized.  For subjects enrolled under Protocol v3.0: The subject does not have a positive RSV diagnostic test at screening, but the subject was randomized.	Selection criteria not met	Inclusion criterion 4 not met: Subject does not have a positive RSV diagnostic test.  Inclusion criterion 4 not met: Subject does not have a positive RSV diagnostic test at screening.
5.	The subject is not expected to stay in the hospital for at least 24 hours (according to the Investigator's judgement at screening), but the subject was randomized.	Selection criteria not met	Inclusion criterion 5 not met: Subject is not expected to stay in hospital for at least 24 hours.
6.	RSV symptoms have appeared more than 4 days before screening date, but the subject was randomized. - or - For subjects enrolled under Protocol v2.0: Since the start of the RSV infection, the RSV symptoms have improved at screening, but subject was randomized.  For subjects enrolled under Protocol v3.0: Since the start of the RSV infection, the RSV symptoms have improved at screening or randomization, but subject was randomized.	Selection criteria not met	Inclusion criterion 6 not met: RSV symptoms appeared more than 4 days prior to screening - or - Inclusion criterion 6 not met: RSV symptoms have improved at screening.  Inclusion criterion 6 not met: RSV symptoms have improved at screening or randomization.
7.	For subjects enrolled under Protocol v2.0: Subject does not fulfill at least two of the three RSV disease severity criteria: - Inadequate oral feeding that requires feeding support - Inadequate oxygen saturation - Signs of respiratory distress, but subject was randomized.  For subjects enrolled under Protocol v3.0: Subject does not fulfill at least two of the three RSV disease severity criteria at screening or randomization: - Inadequate oral feeding that requires feeding support - Inadequate oxygen saturation - Signs of respiratory distress, but subject was randomized.	Selection criteria not met	Inclusion criterion 7 not met: Subject does not fulfill at least two of the RSV disease severity criteria (<specify criteria not fulfilled>).  Inclusion criterion 7 not met: Subject does not fulfill at least two of the RSV disease severity criteria at screening or randomization (<specify criteria not fulfilled>).
8.	Subject does not have a normal psychomotor development, but subject was randomized.	Selection criteria not met	Inclusion criterion 8 not met: Subject does not have a normal psychomotor development.

CONFIDENTIAL

Sequence No.	Description	Protocol Deviation Coded Term (DVDECOD)	Protocol Deviation Term (DVTERM)
11.	The subject has 1 or more significant comorbidity(ies), but subject was randomized.	Selection criteria not met	Exclusion criterion 1 met: Subject is known to have significant comorbidity(ies) (<specify comorbidity>).
12.	The subject is known to be human immunodeficiency virus (HIV)-positive, but subject was randomized. - or - The subject is < 6 months of age and the mother is known to be HIV-positive, but subject was randomized.	Selection criteria not met	Exclusion criterion 2 met: Subject is known to be HIV-positive. - or - Exclusion criterion 2 met: Subject is less than 6 months old and subject's mother is known to be HIV-positive.
13.	The HIV status of the subject is unknown at screening. The subject is HIV-positive as confirmed by a local laboratory test performed at screening, but subject is randomized. - or - The subject is < 6 months of age and the mother is HIV-positive as confirmed by a local laboratory test performed at screening, but subject is randomized.  Only applicable for subjects participating under: - CTP 1.0 - South Africa v1.0 dd. 04/AUG/2016	Selection criteria not met	Exclusion criterion 2 met: Subject is HIV-positive, as confirmed by a local lab test at screening. - or - Exclusion criterion 2 met: Subject is less than 6 months old and subject's mother is HIV-positive as confirmed by a local lab test at screening.
15.	The subject is known to be immunocompromised, but subject was randomized.	Selection criteria not met	Exclusion criterion 3 met: Subject is known to be immunocompromised.
16.	The subject has or is suspected to have an active clinically relevant concurrent infection, but subject was randomized.	Selection criteria not met	Exclusion criterion 4 met: Subject has an active clinically relevant concurrent infection (<specify disease>).
17.	The subject has significant oral and/or maxillofacial malformations which prevent proper positioning of the face mask, but subject was randomized.	Selection criteria not met	Exclusion criterion 5 met: Subject has significant oral and/or maxillofacial malformations.
18.	The subject has received invasive mechanical ventilation or non-invasive respiratory support in the 4 weeks prior to screening, but subject was randomized.	Selection criteria not met	Exclusion criterion 6 met: Subject has received invasive mechanical or non-invasive respiratory support in the 4 weeks prior to screening.
19.	During the current hospital admission, the subject is initially hospitalized in ICU setting and/or the subject received invasive mechanical ventilation, non-invasive respiratory support, but subject was randomized.	Selection criteria not met	Exclusion criterion 7 met: Subject was initially hospitalized in ICU and/or subject received invasive mechanical ventilation, non-invasive respiratory support
20.	The subject is critically ill, but subject was randomized. - or - The subject is expected to require invasive mechanical ventilation, non-invasive respiratory support or High Flow oxygen therapy (HFOT) at levels not enabling nebulization therapy, but subject was randomized.	Selection criteria not met	Exclusion criterion 8 met: Subject was critically ill. - or - Exclusion criterion 8 met: Subject is expected to require (non-) invasive ventilation at levels not enabling nebulization therapy.
21.	The subject has received 1 or more doses of palivizumab or treatment or prophylaxis with any RSV antiviral compound at any time prior to screening, but subject was randomized. - or - The subject's mother has been vaccinated against RSV prior to screening, but subject was randomized.	Selection criteria not met	Exclusion criterion 9 met: Subject has received treatment or prophylaxis with any RSV antiviral compound at any time prior to screening. - or - Exclusion criterion 9 met: Subject's mother has been vaccinated against RSV prior to screening.
22.	The subject is required to continue or start systemic corticosteroid therapy, but subject was randomized.	Selection criteria not met	Exclusion criterion 10 met: Subject is required to continue or start systemic corticosteroid therapy.

CONFIDENTIAL

Sequence No.	Description	Protocol Deviation Coded Term (DVDECOD)	Protocol Deviation Term (DVTERM)
24.	The subject is currently participating in any other study with investigational drug, but subject was randomized. - or - The subject has received an investigational drug within 4 weeks or 5 half-lives of the concerned drug (whichever is longer) prior to screening, but subject was randomized.	Selection criteria not met	Exclusion criterion 12 met: Subject is participating in another study with investigational drug. -or- Exclusion criterion 12 met: Subject has received an investigational drug within 4 weeks or 5 half-lives of the concerned drug prior to screening.
25.	The subject was previously enrolled in a clinical study of ALX-0171 (including ALX0171-C201), but subject was randomized.	Selection criteria not met	Exclusion criterion 13 met: Subject was previously enrolled in a clinical study of ALX-0171.
38.	The first of the 2 serial nebulizations is started successfully but needs to be interrupted, and nebulization could not be completed within 2 hours after nebulizer filling of this nebulization. - or - The second of the 2 serial nebulizations could not be completed within 2 hours after nebulizer filling of this nebulization.	Treatment non-compliance	The <specify type of nebulization> at <specify visit> is interrupted and could not be completed within 2 hours (<specify exact timing>) after filling.
39.	The first of the 2 serial nebulizations was not initiated successfully. - or - The second of the 2 serial nebulizations was not initiated successfully.	Treatment non-compliance	The <specify type of nebulization> at <specify visit> was not initiated successfully.
40.	The first of the 2 serial nebulizations was initiated successfully, but administration was not fully done. - or - The second of the 2 serial nebulizations was initiated successfully, but administration was not fully done.	Treatment non-compliance	The <specify type of nebulization> at <specify visit> could not be completed successfully.
41.	Administration of both serial nebulizations exceeded the maximum time window of 4 hours.	Treatment non-compliance	Study drug administration at <specify visit> exceeded the maximum time window of 4 hours (<specify exact timing>).
43.	Study drugs with rejected IMP were administered to the subject: deviations to the study drug storage conditions occurred, which were not approved by the Sponsor.	Treatment non-compliance	Dosing with rejected IMP: deviations to the study drug storage conditions occurred when study drug was administered to subject (<specify type of nebulization> at <specify visit>).
44.	The dose of study drug was (temporarily) not according to the weight category range, as per protocol.	Treatment non-compliance	A wrong dose (<specify dose>) of study drug was taken on <specify type of nebulization> at <specify visit>.
47.	The subject received study drug administration(s) outside the 24-hour intervals (+/- 4 hours) relative to the first dose (i.e. outside the 24h (+/- 4h) window on Day 2 relative to start of first nebulization on Day 1, or outside the 48h (+/- 4h) window on Day 3 relative to start of first nebulization on Day 1).	Treatment non-compliance	Study drug dosing window deviation: administration outside the 24-hours interval (<specify hours> between <specify type of nebulization> at <specify visit> and first nebulization at Day 1).
48.	The nebulizer is used during study drug administration with a fixed air/O2 flow rate different from 2 L/min.	Treatment non-compliance	Fixed air/O2 flow rate during study drug administration is different from 2 L/min (<specify type of nebulization> at <specify visit>).

CONFIDENTIAL

Sequence No.	Description	Protocol Deviation Coded Term (DVDECOD)	Protocol Deviation Term (DVTERM)
49.	During study drug administration, the face mask is not always (less than 75% of the time) in contact with the face of the subject.	Treatment non-compliance	Face mask is not always in contact with the face of the subject (<specify type of nebulization> at <specify visit>).
50.	The subject has a missed dose without having fulfilled the study drug discontinuation criteria or without having discontinued the study.	Treatment non-compliance	Subject has a missed dose of study drug at <specify visit>.
51.	The study drug was administered by a route other than inhalation.	Treatment non-compliance	Administration of study drug (<specify type of nebulization> at <specify visit>) by a route other than inhalation.
52.	The device number(s) or medication kit number dispensed to the subject was not the same as the number assigned by IWRS.	Treatment non-compliance	<Base unit serial / Inhalation set / Medication kit> number dispensed to subject was not the same as the number assigned by IWRS for <specify type of nebulization> at <specify visit>.
53.	The subject was administered an expired study drug.	Treatment non-compliance	Subject was administered expired study drug (<specify type of nebulization> at <specify visit>).
54.	The subject received oxygen supplementation through a nasal cannula, face mask or headbox, but nasal cannula, face mask or headbox was not removed immediately before study drug administration.	Treatment non-compliance	Nasal cannula, face mask or headbox was not removed before study drug administration (<specify type of nebulization> at <specify visit>).
55.	The subject started treatment with one of the forbidden medications, as defined per protocol, during the study up to the Follow-up visit.	Prohibited concomitant medication	Subject started treatment with forbidden medication during the study up to the Follow-up visit (<specify term, dose, unit, frequency, start and end date, reason administered>).
56.	The subject received hypertonic saline within 4 hours before the start or 4 hours after the end of study drug administration.	Prohibited concomitant medication	Subject received hypertonic saline within 4 hours before start (<specify exact timing>) or 4 hours after end (<specify exact timing>) of study drug administration at <specify visit>.
57.	A planned collection of a nasal mid-turbinate swab was not performed. This should only lead to exclusion from PP population if the missing nasal swab occurred before 2 consecutive BQL values.	Efficacy assessment deviation	Nasal mid-turbinate swab was not collected on <specify timepoint> at <specify visit>.
58.	A planned nasal mid-turbinate swab is taken out of time window. This should only lead to exclusion from PP population if the nasal swab out of time window occurred before 2 consecutive BQL values.	Efficacy assessment deviation	The nasal mid-turbinate swab on <specify timepoint> at <specify visit> was taken out of time window (<specify exact timing>).
70.	The subject is re-hospitalized or consults the Investigator for a respiratory condition after hospital discharge up to EOS visit. At this unscheduled visit, the nasal mid-turbinate swab was not collected. This should only lead to exclusion from PP population if the nasal swab not collected occurred before 2 consecutive BQL values.	Efficacy assessment deviation	The subject is re-hospitalized or consults the Investigator for a respiratory condition, but <specify assessment>
72.	A nasal mid-turbinate swab was collected using an expired kit and/or expired medium. This should only	Efficacy assessment deviation	The nasal mid-turbinate swab on <specify timepoint> at <specify visit> was collected

CONFIDENTIAL

Sequence No.	Description	Protocol Deviation Coded Term (DVDECOD)	Protocol Deviation Term (DVTERM)
	lead to exclusion from PP population if the nasal swab was collected before 2 consecutive BQL values.		using an expired kit and/or medium.
75.	A nasal mid-turbinate swab was collected, but a deviation in the sample storage conditions occurred. This should only lead to exclusion from PP population if the missing nasal swab occurred before 2 consecutive BQL values.	Efficacy assessment deviation	Deviation occurred in sample storage condition of nasal mid-turbinate swab collected on <specify timepoint> at <specify visit>.

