### **3.4.2. BASELINE CHARACTERISTICS**

Demographic and medical history data (including RSV-related signs and symptoms) will be collected at screening.

Collected data will include (but are not limited to): month and year of birth, age (with indication of week level), gender, race (if allowed), and ethnicity (if allowed).

Data on atopy in the family, environmental exposure to tobacco, pets and breastfeeding will also be collected.

The nasal swab sample collected on Day 1 will be used to test for concurrent viruses and the presence of mycoplasma in nasal swab samples. If the volume of the Day 1 pre-dose sample is insufficient, the sample collected after study drug administration can be used for adventitious viral screening.

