### 7.1 Primary Efficacy Endpoint Evaluation

The primary endpoint for this trial is the time needed for the viral load to drop below the plaque assay quantification limit (time-to-BQL) in nasal mid-turbinate swab specimens. Time to BQL is defined as the time from the reference point (first dosing) to the first occurrence of a value below the limit of quantification, provided the next measured value is below the limit as well. The time to event for subjects with missing data and/or who did not reach BQL during the trial will be censored at the last nonmissing viral load assessment .

The time-to-BQL will be compared between each of the ALX-0171 treatment groups and the combined placebo group using a log-rank test. The null hypothesis of this test assumes no difference in time-to-BQL between Placebo and ALX-0171 treated subjects. The tests will be performed in a sequential way to preserve the family-wise error rate at 0.05. Specifically, dose 3 (highest dose) of ALX-0171 will first be tested against the combined placebo group at the 0.05 significance level. Dose 2 of ALX-0171 will only be compared to placebo at the 0.05 significance level if the comparison of dose 3 with placebo is significant. Consequently, dose 1 of ALX-0171 will only be compared to placebo at the 0.05 significance level if the comparison of dose 2 of ALX-0171 with placebo is significant. The primary efficacy endpoint will be evaluated using the mITT population.

The logrank test is based on the assumptions that censoring is unrelated to prognosis and the event probabilities are the same for subjects recruited early and late in the study. Kaplan-Meier (KM) estimates on time-to-BQL will be tabulated (Median, 25th, 75th percentile with confidence interval and general information on censoring) and a graph of the Kaplan-Meier survival curve will be presented.

The data will also be analyzed using a Cox proportional hazards regression model with time to BQL as dependent variable, and treatment group, viral load at baseline and co-infected subject group as independent variables. The hazard ratio (HR) from the Cox model along with the 95% CI will be reported. This analysis will only be performed for the treatment groups where the comparison was significant as analyzed by the log rank test.

For sensitivity analyses, the primary endpoint will also be evaluated using:

- the RSV Infected population
- the Per Protocol population.

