### 19.1.3 Time and events Schedule V3.0

Period Visit	Screening a, b	Study Drug Treatment Period C											In-hospital Post-Treatment Period d	FU visit (Day 14±2) or Withdrawal visit e	EOS e (Day 28±2)
		Hospitalized Dosing								Hospitalized or Ambulatory Dosing					
		Day 1			Day 2			Day 3			Morning and evening				
Approximate time/ Study procedure	-24h to randomization	-3h to dose	Dose	2h (±0.5h)	5h (±1h)	-2h to dose	Dose	2h (±0.5h)	5h (±1h)	-2h to dose		Dose	2h (±0.5h)		
Informed consent	X														
Inclusion/exclusion criteria	X														
RSV diagnosis f	X														
Demographics and medical history	X														
Hospitalization information/Clinical response information g															→
Study drug administration h				X			X				X				
Nasal mid-turbinate swab i		X			X	X			X	X		X	xj	X	
Physical examination k	X	X			X	X			X	X		X	X	X	X
Body weight	X													X	X
Body height	X														
Body temperature	X	X			X	X			X	X		X	X	X	
General appearance	X	X			X	X			X	X		X	X	X	

Period  Visit	Screening a, b	Study Drug Treatment Period C											In-hospital Post-Treatment Period d	FU visit (Day 14±2) or Withdrawal visit e	EOS e (Day 28±2)	
		Hospitalized Dosing									Hospitalized or Ambulatory Dosing					
		Day 1			Day 2			Day 3			Morning and evening					
Approximate time/ Study procedure	-24h to randomization	-3h to dose	Dose	2h (±0.5h)	5h (±1h)	-2h to dose	Dose	2h (±0.5h)	5h (±1h)	-2h to dose	Dose	2h (±0.5h)				
Lung auscultation n	X	X		X	X	X		X	X	X		X	X	X	X	X
Heart rate	X	X		X	X	X		X	X	X		X	X	X	X	
SpO 2 l	X	X		X	X	X		X	X	X		X	X	X		
Feeding m	X	X			X	X			X	X		X	X	X	X	
(Respiratory muscle) retractions	X	X		X	X	X		X	X	X		X	X	X	X	
Respiratory rate	X	X		X	X	X		X	X	X		X	X	X	X	
Randomization b		X														
Daytime coughing	X	X		X	X	X		X	X	X		X	X	X	X	X
(Sleep disturbance from) night-time coughing o	xO	xO				xO				xO				xO	xO	X
Parent/caregiver assessment p																→
Pharmacokinetics (single sample)																←→q
Pharmacokinetics (more extensive sampling)						xr										←→r→←
Clinical laboratory (hematology and clinical biochemistry)	xS, t														xU	
Immunogenicity	xS														xU	
Previous and concomitant medication																→
Adverse events V																→

h = hour; FU = Follow-up; EOS = End of Study.

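### Per-protocol exclusions for swab deviations stop once an infant has two consecutive BQL values, so PP membership depends partly on the outcome (minor; PP analyses only)

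*SAP*

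**What the plan says.** SAP Appendix C (section 19.3) lists the deviations that remove an infant from PP. Five rows concern nasal swabs, and each is limited by the infant's BQL status:

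- Row 57, planned swab not taken: "This should only lead to exclusion from PP population if the missing nasal swab occurred before 2 consecutive BQL values".
- Row 58, swab outside its window: "This should only lead to exclusion from PP population if the nasal swab out of time window occurred before 2 consecutive BQL values".
- Row 70, no swab at an unscheduled respiratory visit: "This should only lead to exclusion from PP population if the nasal swab not collected occurred before 2 consecutive BQL values".
- Row 72, expired kit or medium, which may only "lead to exclusion from PP population if the nasal swab was collected before 2 consecutive BQL values".
- Row 75, storage problem, with the same BQL condition attached: "a deviation in the sample storage conditions occurred. This should only lead to exclusion from PP population if the missing nasal swab occurred".

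No other row of Appendix C has such a condition.

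SAP 7.1 counts time-to-BQL from the first dose, and its event is "the first occurrence of a value below the limit of quantification, provided the next measured value is below the limit as well". Primary analysis is in mITT, and the RSV Infected and PP populations are its two sensitivity analyses. SAP 7.2.1 also runs the Global Severity Score (GSS) mixed model in PP. Both PP results are flagged as topline (Tables 14.2.1.3 and 14.2.1.6).

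SAP 5.1.6 and 6.2 give the reason for the list: PP leaves out deviations that could affect the primary endpoint. SAP 6.2 has the deviation list finalised before database lock.

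**The concern.** A pair of consecutive BQL values is in substance the primary event, so reaching the outcome ends an infant's exposure to exclusion. The same missed Day 3 swab removes an infant who is still shedding and leaves in one who has already cleared. The retained set is therefore enriched for early clearers. If the drug works, the placebo arm holds more slow clearers and is trimmed harder.

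At stake is how well the PP analysis shows that the primary result is robust to deviations. The condition is also loosely worded. Row 75 calls a collected swab *missing*. No row says whether a deviation between the two BQL swabs counts as *before*, or names the assay. Two programmers could build different PP sets.

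**Working it through.** **Exposure.** The "Nasal mid-turbinate swab" row of the version 3.0 schedule (SAP 19.1.3) has a Day 1 pre-dose swab, five post-dose swabs to Day 3, a discharge-day swab for infants still in hospital after treatment, and Day 14. Protocol 3.4.2 confirms the first of these ("If the volume of the Day 1 pre-dose sample is insufficient"). That is 7 planned swabs, or 8 with the discharge swab. An infant who is quantifiable at baseline and clears at the first post-dose swab is exposed at 3 swabs: pre-dose, clearing and confirming. An infant not clear by Day 3 is exposed at all 7 or 8.

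**The plan's own scenario.** SAP 4.2 gives 45 per arm, 15% drop-out, medians of 0.5 and 1 day, and 85% power. Exponential times give a hazard ratio (HR) of 1/0.5 = 2. Events are 2 × 45 × 0.85 = 76.5. Schoenfeld power is Φ(√(76.5/4) × ln 2 − 1.96) = Φ(1.07) = 0.858, so the stated 85% is reproduced. I use HR 2 as the truth below and do not question it.

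**Assumptions not in the documents.** Deviations are independent, occur at q = 2, 5 or 10% per swab, and are equally common in both arms. Post-dose swabs fall at 5.4, 23, 29.4, 47 and 50.4 h. Every infant is quantifiable at baseline. Only swab exclusions are counted, not the other Appendix C rows or drop-out.

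**Clearance probabilities.** With S(t) = 2^(−t/m), the first cell is 1 − 2^(−5.4/12) = 0.268 for active and 1 − 2^(−5.4/24) = 0.144 for placebo. In full:

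- Active (m = 12 h): 0.268, 0.467, 0.082, 0.117, 0.012; not clear 0.054.
- Placebo (m = 24 h): 0.144, 0.341, 0.087, 0.170, 0.024; not clear 0.233.

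**Retention.** An infant clearing at post-dose swab k is kept with probability (1−q)^(k+2), and one not clear by Day 3 with (1−q)^7 or (1−q)^8. For active at 5% with 7 swabs: 0.268 × 0.95³ + 0.467 × 0.95⁴ + 0.082 × 0.95⁵ + 0.117 × 0.95⁶ + (0.012 + 0.054) × 0.95⁷ = 0.806. Placebo gives 0.774. I then rescaled the kept cells and fitted a grouped complementary log-log model, which returns 2.00 with no exclusions.

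| q | Kept, active/placebo (7 swabs) | PP HR (7) | Kept (8 swabs) | PP HR (8) | Placebo still quantifiable at Day 2 pre-dose (7; true 51.5%) |
|---|---|---|---|---|---|
| 2% | 92/90% | 1.98 | 92/90% | 1.97 | 50.1% |
| 5% | 81/77% | 1.95 | 80/77% | 1.93 | 48.1% |
| 10% | 64/59% | 1.89 | 64/58% | 1.85 | 44.6% |

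The standard error of log HR after exclusions is 0.25 to 0.30. The largest shift is ln(2/1.853) = 0.076, about a quarter of a standard error. At 5% with 7 swabs it is ln(2/1.946) = 0.027, about a tenth.

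**Where it arises.** Restricting deviations to the first three planned swabs leaves HR at 2.00. Restricting them to the Day 2 5-hour swab and later reproduces 1.98/1.95/1.89, the whole effect.

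**The other reading of *before*.** If a deviation between the two BQL swabs does not count, the exponent is k+1 and HR is 1.97/1.93/1.85 (7) or 1.96/1.91/1.82 (8).

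**Type I error.** A separate simulation used 45 per arm, missed swabs only and slightly different swab times. With no true effect, the PP log-rank test rejected in 0.051 to 0.055 of trials. At 5% per swab and a 24 h median, the rule excluded 17.6% of faster and 29.7% of slower clearers.

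**The case against.** The strongest defence is that the rule follows the SAP's own definition. A swab deviation after confirmed clearance cannot change time-to-BQL, so under SAP 5.1.6 it should not exclude. The rule is prespecified, the bias is small and conservative, every figure above rests on an assumed deviation rate, and no formal test uses PP.

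Most of that stands, and it is why the point is minor. But the argument only shows that a late deviation is harmless to one infant's event time. It does not stop the retained set from being selected on clearance.

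A reader might infer more than the documents support:

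- That the primary result is at risk. It is not: the primary test and its hierarchy use mITT, and the RSV Infected analysis has no swab exclusions.
- That the rule favours the drug or inflates false positives. With equal deviation rates the HR moves towards 1, and simulated type I error stays near 0.05.
- That early deviations can never select. This holds only if every infant has a quantifiable plaque titre at baseline, which SAP 5.1.4 and 5.1.6 do not require. The gap is very small: with an assumed 10% BQL at baseline and 5% deviations at the first three swabs only, HR moves from 1.857 to 1.851.

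**Conclusion.** The point holds as a minor one. Rows 57, 58, 70, 72 and 75 make PP membership depend partly on the primary outcome: slow clearers are excluded more often and PP clearance times are biased short. The reach is the PP sensitivity analysis of the primary endpoint and the PP run of the GSS model. I have not sized the effect on GSS.

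For the primary endpoint, the attenuation from 2.00 is at most to about 1.85 (1.82 on the other reading of *before*), and that needs a 10% deviation rate per swab. The sizes depend on exponential clearance and on independent deviations that are equally common in both arms. The existence of the selection does not depend on those rates, provided some deviations fall at the Day 2 5-hour swab or later.

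**What to change.** - Remove rows 57, 58 and 70 from the PP exclusion list. Keep those infants and time them by the SAP 7.1 next-measured-value rule at actual swab times, which Protocol 3.4.3.1 already records. Out-of-window swabs keep their values and times.
- For rows 72 and 75, keep the infant and treat the affected result as missing in the PP sensitivity analysis only. State that mITT data handling does not change, and that an infant's event time may therefore differ between PP and mITT.
- Correct *missing* in row 75, and define *before* if any such wording remains.

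The cost is Appendix C wording plus a short data-handling statement. Out-of-window swabs cost nothing. Infants with a missed or invalid swab are timed slightly late or may be censored. In a simulation of 400,000 infants per arm (Monte Carlo error of HR about 0.005), with every deviation a missing value, HR was 1.99/1.99/1.96 at 2/5/10% with 7 swabs and 1.99/1.97/1.94 with 8. With 7 swabs the placebo restricted mean to 96 h moved +0.6/+1.5/+2.8%, against −1.7/−5.2/−10.1% under the present rule. The PP set for the GSS model also becomes larger, which should be stated.

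I would not instead apply the exclusions to a fixed set of swabs regardless of clearance. That would drop infants for deviations that cannot affect the endpoint, contrary to SAP 5.1.6.
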